5.0 Stratification Factors

- 5.1 Patient age: ≥ 65 years vs. < 65 years
- 5.2 Splenectomy and/or rectosigmoid resection: yes vs. no
- 5.3 Optimally debulked cancer (complete nodal and omental removal, as appropriate, with <1 cm of residual tumor, if appropriate): yes vs. no
- 5.4 Cancer type: ovarian vs. endometrial vs. other
- 5.5 Open laparotomy vs. laparoscopic surgery

6.0 Registration/Randomization Procedures**6.1 Registration Procedures**

- 6.11 To register a patient, access the Mayo Clinic Cancer Center (MCCC) web page and enter the registration/randomization application. The registration/randomization application is available 24 hours a day, 7 days a week. Back up and/or system support contact information is available on the Web site. If unable to access the Web site, call the MCCC Registration Office at [contact] between the hours of 8 a.m. and 4:30 p.m. Central Time (Monday through Friday).

The instructions for the registration/randomization application are available on the MCCC web page (<http://hsrwww.mayo.edu/ccs/training>) and detail the process for completing and confirming patient registration. Prior to initiation of the protocol intervention, this process must be completed in its entirety and a MCCC subject ID number must be available as noted in the instructions. It is the responsibility of the individual registering the patient to confirm the process has been successfully completed prior to release of the study agent. Patient registration via the registration/randomization application can be confirmed in any of the following ways:

- Contact the MCCC Registration Office [contact]. If the patient was fully registered, the MCCC Registration Office staff can access the information from the centralized database and confirm the registration.
- Refer to “Instructions for Remote Registration” in section “Finding/Displaying Information about A Registered Subject.”

- 6.12 A mandatory baseline correlative research component is part of this study, the patient will be automatically registered onto this component (see Sections 3.19 and 14.1).

An optional correlative research component is part of this study, there will be an option to select if the patient is to be registered onto this component (see Section 14.0)

- Patient has/has not given permission to give his/her blood sample(s) for research testing for Cycles 2 and 3

6.13 Documentation of IRB approval must be on file in the Registration Office before an investigator may register any patients.

In addition to submitting initial IRB approval documents, ongoing IRB approval documentation must be on file (no less than annually) at the Registration Office ([contact]). If the necessary documentation is not submitted in advance of attempting patient registration, the registration will not be accepted and the patient may not be enrolled in the protocol until the situation is resolved.

When the study has been permanently closed to patient enrollment, submission of annual IRB approvals to the Registration Office is no longer necessary.

6.14 Prior to accepting the registration, the registration/randomization application will verify the following:

- IRB approval at the registering institution
- Patient eligibility
- Existence of a signed consent form
- Existence of a signed authorization for use and disclosure of protected health information

6.15 Intervention on this protocol must commence at Mayo Clinic Rochester, under the supervision of a medical oncologist.

6.16 Intervention cannot begin prior to registration and must begin \leq 7 days after registration.

6.17 Pre-intervention tests/procedures (see Section 4.0) must be completed within the guidelines specified on the test schedule.

6.18 All required baseline symptoms (see Section 10.6) must be documented and graded.

6.19a Study agent is available on site

6.19b Blood draw kit is available on site.

6.19c Patient questionnaire booklet is available on site; copies are not acceptable for this submission.

6.19d At the time of randomization, the following will be verified:

- Patient has/not given permission for his/her blood sample(s) to be stored and used in future research of ovarian cancer at Mayo Clinic.
- Patient has/not given permission for his/her blood sample(s) to be stored and used in future research at Mayo Clinic to learn about, prevent, or treat any other health problems
- Patient has/not given Mayo Clinic permission to give his/her blood sample(s) to outside institutions

6.2 Randomization Procedures

6.21 The factors defined in Section 5.0 will be used as stratification factors.

6.22 After the patient has been registered into the study, the values of the stratification factors will be recorded, and the patient will be assigned to one of the following intervention groups using the Pocock and Simon dynamic allocation procedure which balances the marginal distributions of the stratification factors between the intervention groups [16].

- Oral Serum Bovine Immunoglobulin (SBI)
- Placebo

6.3 Procedures for Double-Blinding the Intervention Assignment

6.31 After the intervention assignment has been ascertained by the registration/randomization application, the patient's study medication code number will be displayed on the confirmation of registration screen.

6.32 The data manager/nurse/pharmacist at the patient's institution must contact the MCCC Registration Office for a code number when additional study product is needed for the patient.

6.33 The number of the intervention bottle/packet assigned to the patient will be recorded on the dosing form.

6.34 MCCC Registration Office personnel will monitor the supply of coded bottles/packets at each participating institution and will arrange for the oncology pharmacist to send further supplies to the participating institutions as needed.

7.0 Protocol Intervention

7.1 Dosing Intervention Schedule**

Agent	Dose	Route	Day	Retreat
Serum bovine immunoglobulin or placebo packets	5 grams (1-packet) per each dose*	PO	Twice a day for 12 weeks (3 cycles)	Every 4 weeks

*total dose is 10 grams per day

** Patients must begin taking agent/placebo within 7 days of registration (exceptions can be made if delays occur related to shipping agent/placebo and should be documented in the patient study record).

7.2 Patients can be instructed in administration techniques and granted intervention independence with nursing staff approval.

7.3 Patients will be instructed to add the contents of one packet (5 grams) to a cup and dissolve the powder with approximately one-half cup (4 fl. ounces, or 120 mL) of water. The patient will stir to mix and drink the contents. The patient will take one dose twice a day, in the morning and evening, with or without food.

7.4 Breaking Codes in Double-Blinded Studies-The intervention code may *not* be broken except for emergencies.

In the event of an emergency, call the MCCC Registration Office at [contact] to break the code on Monday through Friday, 8:00 a.m. to 4:30 p.m. Central Time. If the code must be broken after hours, assume the patient was assigned to active treatment and treat accordingly. Place a call to the MCCC Registration Office and leave a message informing them of the need to un-blind a patient. Provide your contact information so that MCCC Registration Office personnel can return the call the next business day.

8.0 Dosage Modification Based on Adverse Events

There are no dose modifications in this trial. If the patient experiences a grade 1 or worse adverse event that is thought to be related to the study intervention, the patient should discontinue the intervention and proceed to the 4 week post intervention observation.

9.0 Ancillary Treatment/Supportive Care

9.1 Antiemetics may be used at the discretion of the attending physician.

9.2 Blood products and growth factors should be utilized as clinically warranted and following institutional policies and recommendations. The use of growth factors should follow published guidelines of the American Society of Clinical Oncology 2006 Update of Recommendations for the Use of White Blood Cell Growth Factors: An Evidence-Based Clinical Practice Guideline *J Clin Oncol* 24(19): 3187-3205, 2006.

9.3 Patients should receive full supportive care while on this study. This includes blood product support, antibiotic treatment, and treatment of other newly diagnosed or concurrent medical conditions. All blood products and concomitant medications such as antidiarrheals, analgesics, and/or antiemetics received from the first day of study intervention administration until 30 days after the final dose will be recorded in the medical records.

10.0 Adverse Event (AE) Reporting and Monitoring

10.1 Adverse Event Characteristics

CTCAE term (AE description) and grade: The descriptions and grading scales found in the revised NCI Common Terminology Criteria for Adverse Events (CTCAE) version 4.0 will be utilized for AE reporting. All appropriate treatment areas should have access to a copy of the CTCAE version 4.0. A copy of the CTCAE version 4.0 can be downloaded from the CTEP web site:

(http://ctep.cancer.gov/protocolDevelopment/electronic_applications/ctc.htm)

10.11 Adverse event monitoring and reporting is a routine part of every clinical trial. First, identify and grade the severity of the event using the CTCAE version 4.0. Next, determine whether the event is expected or unexpected (see Section 10.2)

and if the adverse event is related to the medical intervention or procedure (see Section 10.3). With this information, determine whether the event must be reported as an expedited report (see Section 10.4). Expedited reports are to be completed within the timeframes and via the mechanisms specified in Sections 10.4. All AEs reported via expedited mechanisms must also be reported via the routine data reporting mechanisms defined by the protocol (see Sections 10.52 and 18.0).

10.12 Each CTCAE term in the current version is a unique representation of a specific event used for medical documentation and scientific analysis and is a single MedDRA Lowest Level Term (LLT). Grade is an essential element of the Guidelines and, in general, relates to **severity** for the purposes of regulatory reporting to NCI.

NOTE: A severe AE, as defined by the above grading scale, is **NOT** the same as serious AE which is defined in the table in Section 10.4.

10.2 Expected vs. Unexpected

- The determination of whether an AE is expected is based on the agent-specific information provided in Section 15.0 of this protocol.
- Unexpected AEs are those not listed in the agent-specific information provided in Section 15.0 of this protocol.

NOTE: “Unexpected adverse experiences” means any adverse experience that is neither identified in nature, severity, or frequency of risk in the information provided for IRB review nor mentioned in the consent form.

10.3 Assessment of Attribution

When assessing whether an adverse event is related to a medical treatment or procedure, the following attribution categories are utilized:

Definite - The adverse event is *clearly related* to the agent(s).
Probable - The adverse event is *likely related* to the agent(s).
Possible - The adverse event *may be related* to the agent(s).
Unlikely - The adverse event is *doubtfully related* to the agent(s).
Unrelated - The adverse event is *clearly NOT related* to the agent(s).

Events determined to be possibly, probably or definitely attributed to a medical intervention suggest there is evidence to indicate a causal relationship between the agent and the adverse event.

10.4 Expedited Reporting Requirements for Commercial Agent(s) ONLY:

Expedited Reporting Requirements for Adverse Events that Occur in a Non-IND/IDE trial within 30 Days of the Last Administration of a Commercial Agent^{1,2}

ALL SERIOUS adverse events that meet the above criteria **MUST** be immediately reported to the sponsor within the timeframes detailed in the table below.

Hospitalization	Grade 1 Timeframes	Grade 2 Timeframes	Grade 3 Timeframes	Grade 4 & 5 Timeframes
Resulting in Hospitalization ≥ 24 hrs		7 Calendar Days		24-Hour 3 Calendar Days
Not resulting in Hospitalization ≥ 24 hrs	Not required		7 Calendar Days	

NOTE: Protocol specific exceptions to expedited reporting of serious adverse events are found in section 10.41 of the protocol.

Expedited AE reporting timelines are defined as:

- “24-Hour; 3 Calendar Days” - The AE must initially be reported via MedWatch within 24 hours of learning of the AE, followed by a complete expedited report within 3 calendar days of the initial 24-hour report.
- “7 Calendar Days” - A complete expedited report on the AE must be submitted within 7 calendar days of learning of the AE.

¹Serious adverse events that occur more than 30 days after the last administration of investigational agent/intervention and have an attribution of possible, probable, or definite require reporting as follows:

Expedited 24-hour notification followed by complete report within 3 calendar days for:

- All Grade 4, and Grade 5 AEs

Expedited 7 calendar day reports for:

- Grade 2 adverse events resulting in hospitalization or prolongation of hospitalization
- Grade 3 adverse events

Effective Date: May 5, 2011

Additional Instructions:

1. An increased incidence of an expected adverse event (AE) is based on the patients treated for this study at their site. A list of known/expected AEs is reported in the package insert or the literature, including AEs resulting from an agent overdose.
2. Mayo Clinic Cancer Center (MCCC) Institutions: Use FDA Medwatch (Form 3500A) available in forms packet for Investigational agents or commercial/investigational agents on the same arm. Submit to Entera Health, Inc. within 24 hours of notification to: [contact] and [contact].*

*Note: FDA Submission will not occur due to GRAS status of SBI - See [Appendix VII](#)

Event Type	REPORTING PROCEDURE
Other Grade 4 or 5 Events and/or Any Hospitalizations During Treatment Not Otherwise Warranting an Expedited Report	
Complete a Notification Form: Grade 4 or 5 Non-AER Reportable Events/Hospitalization Form electronically via the MCCC Remote Data Entry System or paper form within 5 working days of the date the clinical research associate (CRA) is aware of the event(s) necessitating the form.
 
If an expedited written report has been submitted, this form does not need to be submitted.

10.41 Special Situations for Expedited Reporting

Exceptions to Expedited Reporting: EXPECTED Serious Adverse Events

An expedited report may not be required for specific Grade 1, 2 and 3 Serious Adverse Events where the AE is **EXPECTED**. Any protocol specific reporting procedures **MUST BE SPECIFIED BELOW** and will supersede the standard Expedited Adverse Event Reporting Requirements:

System Organ Class (SOC)	Adverse event/Symptoms	CTCAE Grade at which the event will not be expeditedly reported.
Blood and lymphatic system disorders	Hemoglobin decreased	≤Grade 2
	Lymphocyte count decreased	≤Grade 2
Investigations	Neutrophil count decreased	≤Grade 2
	Platelet count decreased	≤Grade 2
	White blood cell decreased	≤Grade 2

Specific protocol exceptions to expedited reporting should be reported expeditiously by investigators **ONLY** if they exceed the expected grade of the event.

10.5 Other Required Reporting

10.51 Persistent or Significant Disabilities/Incapacities

Any AE that results in persistent or significant incapacity or substantial disruption of the ability to conduct normal life functions (formerly referred to as disabilities), congenital abnormalities or birth defects, must be reported immediately to the study team.

10.52 Death

Any death occurring within 30 days of the last dose, regardless of attribution to an agent/intervention requires expedited reporting within 24-hours to the study team.

Any death occurring greater than 30 days with an attribution of possible, probable, or definite to an agent/intervention requires expedited reporting within 24-hours to the study team.

Reportable categories of Death

- Death attributable to a CTCAE term.
- Death Neonatal: A disorder characterized by cessation of life during the first 28 days of life.
- Death NOS: A cessation of life that cannot be attributed to a CTCAE term associated with Grade 5.
- Sudden death NOS: A sudden (defined as instant or within one hour of the onset of symptoms) or an unobserved cessation of life that cannot be attributed to a CTCAE term associated with Grade 5.
- Death due to progressive disease should be reported as **Grade 5 “Neoplasms benign, malignant and unspecified (incl cysts and polyps) – Other (Progressive Disease)”** under the system organ class (SOC) of the same name. Evidence that the death was a manifestation of underlying disease (e.g., radiological changes suggesting tumor growth or progression; clinical deterioration associated with a disease process) should be submitted.

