10.6 Required Routine Reporting

Adverse events to be graded at each evaluation and preintervention symptoms/conditions to be evaluated at baseline per the CTCAE v4.0 grading unless otherwise stated in the table below:

System Organ Class (SOC)	Adverse event/Symptoms	Baseline	Each evaluation
Gastrointestinal disorders	Abdominal pain	X	X
	Bloating	X	X
	Diarrhea		X
	Baseline number of stools per day	X	
	Flatulence	X	X
	Nausea	X	X
	Vomiting	X	X
General disorders and administration site conditions	Fatigue	X	X
Infections and infestations	Wound infection	X	X
Injury, poisoning and procedural complication	Wound complication	X	X
	Wound dehiscence	X	X

10.61 Submit via appropriate MCCC Case Report Forms (i.e., paper or electronic, as applicable) the following AEs experienced by a patient and not specified in Section 10.6

10.611 Grade 2 AEs deemed *possibly, probably, or definitely* related to the study intervention or procedure.

10.612 Grade 3 and 4 AEs regardless of attribution to the study intervention or procedure.

10.613 Grade 5 AEs (Deaths)

10.6131 Any death within 30 days of the patient's last study treatment or procedure regardless of attribution to the study intervention or procedure.

10.6132 Any death more than 30 days after the patient's last study intervention or procedure that is felt to be at least possibly intervention related must also be submitted as a Grade 5 AE, with a CTCAE type and attribution assigned.

11.0 Intervention Evaluation: None**12.0 Descriptive Factors: None****13.0 Follow-up Decision at Evaluation of Participants**

- 13.1 Participants will receive 3 cycles of therapy (12 weeks) with oral SBI or placebo, followed by a 4 week observation visit. No additional follow-up is required for these patients beyond the 4 week observation time point.
- 13.2 Participants who go off the intervention early for unacceptable adverse events or patient refusal of further treatment will go to the observation phase. Patients can continue in the observation phase for total of 16 weeks of study participation.
- 13.3 Participants where post-operative problems occur, study treatment cannot begin, and participant agrees to complete questionnaires will crossover to QOL assessment only. These participants will be followed per the test schedule (Section 4.0).

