We expect about 10% of patients to experience grade 3 or worse adverse events (at least possibly related to the study intervention). In addition, we expect less than 1% of patients to experience a Grade 5 adverse event, at least possibly related to the study intervention. Accrual will be temporarily suspended to this study if at any time we observe adverse events that satisfy any of the following within each arm separately (i.e. if any of the following occur in arm A or arm B, we will suspend accrual to the trial):

- If at any time 4 or more in the first 20 treated patients (or 20% or more after the first 20) experience a Grade 3 or worse adverse event (possibly, probably, or definitely related to the intervention).
- If at any time, 1 patient experiences a grade 5 adverse event (possibly, probably, or definitely related to the intervention).

We note that we will review all Grade 5 adverse events on a case-by-case basis as well (regardless of attribution), and may suspend accrual after just one Grade 5 event, if we feel it is necessary for patient safety.

16.6 Definitions and Analyses of Secondary Endpoints: All these endpoints will be assessed individually and will also be compared between the 2 arms. Monthly phone calls may be used to collect the secondary endpoint information for each patient, including adverse events, surgical complications, and other data (e.g. patient reported weight, intervention compliance, etc.). We will be assessing, reporting on, and potentially analyzing all the data collected from these monthly telephone calls.

16.61 Adverse Events: All eligible patients who have initiated therapy will be considered evaluable for adverse event analyses. The maximum grade for each type of adverse event will be recorded for each patient up to 16 weeks post-randomization (12 weeks of intervention + 1 month post-intervention observation timepoint), and frequency tables will be reviewed to determine adverse event

patterns. The overall adverse event rates for grade 2 or higher adverse events, will be compared using Chi-Square or Fisher's Exact tests. In addition, the surgical complication rates (up to 1 month post-surgery) will also be compared between the 2 arms using Chi-Square or Fisher's Exact tests.

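### For patients who stop the intervention early, the death-submission rules in 10.52 and 10.613 are narrower than the Grade 5 review and 16-week tabulation promised in 16.51, 16.52 and 16.61

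*Combined protocol and SAP*

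**What the plan says.** **Submission rules.** Under Section 10.52, "Any death occurring within 30 days of the last dose, regardless of attribution to an agent/intervention" goes to the study team within 24 hours. After 30 days the duty is conditional: "Any death occurring greater than 30 days with an attribution of possible, probable, or definite to an agent/intervention requires expedited reporting". The routine rule has the same shape. Section 10.6131 takes all deaths in the first 30 days, and 10.6132 covers a death more than 30 days after the "last study intervention or procedure that is felt to be at least possibly intervention related must also be submitted as a Grade 5 AE". For non-fatal events, Section 10.612 asks for "Grade 3 and 4 AEs regardless of attribution to the study intervention or procedure" and states no time limit.

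**Monitoring and analysis.** Section 16.51 says the study team hears of every grade 4 and 5 event as it happens. Section 16.52 adds: "we will review all Grade 5 adverse events on a case-by-case basis as well (regardless of attribution". Section 16.61 says: "The maximum grade for each type of adverse event will be recorded for each patient up to 16 weeks post-randomization". It limits the adverse event population to eligible patients who started therapy.

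**Follow-up.** Section 13.2 lets patients who stop early remain in observation up to 16 weeks in total. Section 8.0 sends a patient who stops for a related adverse event to a 4-week observation. Section 13.3 keeps willing patients who never start for quality-of-life (QOL) assessment only, and a footnote in 18.12 says no adverse events are collected for them.

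**Other route.** Section 10.4 has a notification form for "Other Grade 4 or 5 Events and/or Any Hospitalizations During Treatment Not Otherwise Warranting an Expedited Report". Section 18.12 lists it as due at each occurrence.

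**The concern.** The statistical section describes a Grade 5 review that ignores attribution and an adverse event table that runs to a fixed time after randomization. The rules telling sites what to submit run on a different clock, which starts at the patient's own last dose and after 30 days depends on the investigator's attribution. For a full course the two clocks agree. For an early stopper they separate.

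The rule for deaths is also narrower than the one for non-fatal events. In an early stopper, an unrelated grade 4 event at week 10 must be submitted under 10.612. If the same event ends in death, 10.613 does not require it.

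At stake is whether the case-by-case Grade 5 review and the 16-week maximum-grade table are complete, and whether they are equally complete in both arms. Section 8.0 stops the intervention for any related adverse event of grade 1 or worse, so early stopping is built into the design and could differ by arm.

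**Working it through.** **Plan's own window.** Sections 13.1 and 16.61 give 12 weeks of intervention plus a 4-week (one-month) observation: 84 + 28 = 112 days = 16 weeks. The stated 16 weeks is reproduced.

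**Time outside the any-attribution rule.** Let L be the day of the last dose, counted from randomization. Deaths of any attribution must be submitted to day L + 30. The rest of the window is max(0, 112 − (L + 30)) = max(0, 82 − L).

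| Last dose (day) | Any-attribution cover ends (day) | Days outside | Share of 112 |
|---|---|---|---|
| 7 | 37 | 75 | 67% |
| 28 | 58 | 54 | 48% |
| 56 | 86 | 26 | 23% |
| 84 (full course) | 114 | 0 | 0% |

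Section 6.16 lets the intervention start up to 7 days after registration, so a full course may end as late as day 91. Cover then runs to day 121, again with no gap.

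**Two readings that change the table.**
- Section 10.613 counts from the last intervention *or procedure*; 10.52 counts from the last dose. Procedure is not defined. If it includes study assessments such as the weekly questionnaires, the routine-reporting gap shrinks or closes.
- If 8.0 is taken literally, a patient stopping for a related event is followed for 28 days, which lies inside the 30-day rule. There is then no gap within her follow-up, but follow-up ends at day L + 28, before day 112 for any L below 84.

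**Patients who never start.** Three statements combine: 13.3 follows them for QOL, 18.12 collects no adverse events, and 16.61 leaves them out of the adverse event population. A clock that starts at the last dose does not exist for them. No passage says where their death would be recorded.

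**How many deaths.** The documents give neither the number of early stoppers nor 16-week mortality. As an illustration on assumptions only, take 10 to 30 early stoppers, 16-week mortality of 1% to 5% at constant hazard, all deaths unrelated, and 26 to 81 days outside the rule (81 is a last dose on day 1). Expected deaths = stoppers × mortality × days/112:
- low: 10 × 0.01 × 26/112 = 0.02
- high: 30 × 0.05 × 81/112 = 1.08

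**The case against.** The strongest reply is that a reader might infer these deaths go uncounted, and the documents do not show that for patients who started. Section 10.52 governs 24-hour notice, not tabulation. The 10.4 notification form is meant for Grade 4 and 5 events that need no expedited report, which describes such a death, and 18.12 makes it due at each occurrence. In its heading, the words about treatment follow directly on hospitalizations and may limit only those. Sections 4.0 and 18.12 also carry adverse event assessment and the Adverse Event Form into the observation phase. This stands: a site could well report the death by one of these routes. It does not remove the conflict, because 10.6132 is the specific routine rule for deaths and makes submission conditional, while the form's heading can equally be read as covering only the treatment period. Sections 16.51, 16.52 and 16.61 state what will be known or reviewed; they do not instruct sites to submit.

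Three other strong readings also fail:
- *That 10.52 excludes never-starters.* Their omission comes from explicit statements in 18.12 and 16.61.
- *That the stopping rule is compromised.* The defined Grade 5 trigger counts only events at least possibly related, and 10.52 and 10.6132 capture those without time limit. Only the discretionary review regardless of attribution is touched.
- *That the primary result is distorted.* Section 16.11 censors a patient without improvement at her last QOL evaluation whatever the reason, so recording a death would not change the log-rank test.

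It is also fair that 13.2 permits, rather than requires, follow-up to week 16, and that this is a pilot of at most 100 patients.

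**Conclusion.** The conflict is real but limited. For early stoppers who remain in observation, following 10.52 and 10.6132 as written can leave the review promised in 16.52 and the 16-week table in 16.61 incomplete. Counted from the last dose, the period concerned is 82 − L days for a last dose on day L before day 82, and zero from then on. This assumes that follow-up runs to week 16 under 13.2 and that the undefined procedure does not extend the routine clock.

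Separately, never-starters followed for QOL have no stated route for recording death.

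The number of deaths affected cannot be taken from the documents and may be zero. The illustrative 0.02 to 1.08 rests wholly on assumed inputs. The point concerns the completeness of safety data. The correction is worth making because it is cheap.

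**What to change.** - Reconcile 10.52 and 10.613 with 16.51, 16.52 and 16.61. Record the date and cause of any death, regardless of attribution, for every randomized patient still followed, through 16 weeks after randomization or 30 days after the last dose, whichever is later. Keep the attribution condition only beyond that point.
- State that the 18.12 footnote on patients who do not start therapy does not apply to deaths.
- Make clear that, for Grade 5 events, the 10.4 notification form is not confined to the treatment period.
- Tabulate deaths by randomized arm, so that never-starters appear even though they lie outside the adverse event population.
- Reconcile the follow-up lengths in 8.0 and 13.2.

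The cost is protocol wording, a death date and cause on the existing observation form, and a few extra reports of deaths from progressive disease. Sample size and the primary analysis do not change.
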